Demographics

Treatment Group	Participant	Age at Time of screening (years)	Sex	Race / Ethnicity	Visit	Date / Time	Height (cm)	Weight (kg)	BMI (kg/m ²)	Comments
xxxxxx	xxxxxx	xx	Male / Female	xxxxxx / xxxxxx	Screening	ddmmmyyyy / hh:mm	xxx	xx.xx	xx	xxxxxx

NA = Not Applicable.

Note: Results for height, weight and BMI are shown for all visits at which they were recorded.

Programming note: For height, weight, and BMI if recording is repeated, then all sets of results should be shown.

Listing 16.2.4.77
Reproductive Status and Contraceptive Use

Treatment Group	Participant	Sex	Breast Feeding/ Pregnant Recently /	Child-bearing potential?	Agree to not donate sperm	(Hetero) Sexually active?	Agree to contraception	Contraception methods [1]
			Planning Pregnancy					
xxxxxx	xxxxxx	Male	NA	NA	Yes / No	Yes / No	Yes / No	1
xxxxxx	xxxxxx	Female	Yes / No	Yes / No; menopausal / No; incapable	NA	Yes / No	Yes / No	3

[1] 1 Male sterilisation where vasectomised male is the sole partner for that woman.

2 Oral, injected or implanted hormonal methods of contraception (minimum 2 weeks prior to admission).

3 An intrauterine device (IUD) or intrauterine hormone-releasing system (IUS) or bilateral tubal ligation.

4 Male condom with spermicide and female partner using a highly effective method of contraception (e.g. IUD, IUS, bilateral ligation).

5 Other method.

Listing 16.2.4.78
Smoking History

Treatment Group	Participant	Smoking History	Start Date	Stop Date	Date Last Smoked	Category	Amount	Years	Comments
xxxxxxx	xxxxxx	xxxxxxxxxx	ddmmyyyy	ddmmyyyy	ddmmyyyy	Number of cigarettes smoked per day Number of cigars smoked per day Tobacco smoked per week (grams) Pack years	xx xx xx xx	xx xx xx xx	xxxxxxxxxxxx xxxxxxxxxxxx xxxxxxxxxxxx xxxxxxxxxxxx

* Date estimated.

Note: Comments are collected for the combined smoking, alcohol and drugs of abuse module and hence may relate to any of these parameters.

Listing 16.2.4.79
Alcohol Use

Treatment Group	Participant	Alcohol Use History	Weekly alcohol intake (units)	Willing to refrain from alcohol intake	Comments
xxxxxx	xxxxx	Never / Current User / Previous User	xx	Yes / No	xxxxxxxxxx

Note: Comments are collected for the combined smoking, alcohol and drugs of abuse module and hence may relate to any of these parameters.

Listing 16.2.4.80
Recreational Drugs of Misuse

Treatment Group	Participant	Current or recent user of recreational drugs?	Start Date	Stop Date	Recreational drug(s) used	Volume	Route	Comments
xxxxxxx	xxxxxx	Yes / No	ddmmmyyyy*	ddmmmyyyy / hh:mm	XXXX	XXXX	XXXX	XXXX

NA = Not Applicable. * = Date estimated.

Listing 16.2.4.81
Medical History

Treatment Group	Participant	MedDRA SOC / Preferred Term [1] / Medical Condition	Start Date / End Date	Line No.	Frequency	Ongoing	Concomitant medication taken for this condition?
xxxxxx	xxxxxx	Xxxxxxxxxx Xxxxxxxxxx Xxxxxxxxxx	ddmmmyyyy / ddmmmyyyy	xxxx	Single Episode / Intermittent / Continuous / Other	Yes / No	Yes / No

* Date estimated.

[1] MedDRA Version 25.0. The modified term is the term that was used for MedDRA coding of the event when the event required multiple codes.

Listing 16.2.4.82
Prior and Concomitant Medications

Treatment Group	Participant	Drug Class (L2) / WHO Drug Name/ Medication (verbatim) [1]	Start Date / Time	Stop Date / Time	Ongoing	Indication / AE/ Medical History Line	Dose / Dose units	Frequency [2]	Route [3]	PI / P / C [4]
xxxxxx	xxxxxx	Xxxxxxxxxx Xxxxxxxxxx Xxxxxxxxxx	ddmmmyyyy / hh:mm	ddmmmyyyy / hh:mm	Yes / No	Xxxxxxxxxx / Xxxxxxxxxx / Xxxxxxxxxx	XX xx	XXX	XXX	PI

* = Date/time estimated.

[1] WHO Drug Global Version 2022:1, March 1, 2022.

[2] QD = Once a day, BD = Twice a day, PRN = As needed, TDS = Three times a day, QDS = Four times a day.

[3] PO = oral, TOP = topical, PRN = Take as needed.

[4] PI = Prior to Inoculation, P = Prior to IMP treatment and after inoculation, C = Concomitant with IMP treatment.

Note: If the medication stop date is before the date of inoculation the medication will be assigned as prior to inoculation. If the medication stop date is before the date of IMP treatment but after the date of inoculation, the medication will be assigned as being prior to IMP treatment. In all other cases, the medication is assigned as concomitant with IMP treatment.

Listing 16.2.5.83
Challenge Virus Inoculation Administration

Treatment Group	Participant	Administration Date / Time	Administered intranasally?	Administered to both nostrils?	Administered successfully?	Change in health in 30 minutes post administration?	Comments
xxxxxx	xxxxxx	ddmmmyyyy / hh:mm	Yes / No	Yes / No	Yes / No	Yes / No	XXXXXX

Listing 16.2.5.84
Viral Shedding Results

Treatment Group	Participant	Study day and nasal wash time-point	qPCR result	Comments
xxxxxx	xxxxxx	Day X AM/PM	Positive/Negative/Invalid/NA	XXXXXXX
		Day X AM/PM	Positive/Negative/Invalid/NA	XXXXXXX
		... Subject to be dosed Day 5 PM	NA	XXXXXXX

Listing 16.2.5.3
IMP Administration

Treatment Group	Participant	Dose Number	Administered?	Administration Date / Time	Was dose fully administered?	Comments
xxxxxx	xxxxxx	XX	Yes / No	ddmmmyyyy / hh:mm	Yes / No	XXXXXXXX

Listing 16.2.6.1.1
Viral Load by Nasal Samples qRT-PCR Results

Treatment Group	Participant	Sample Collection Date / Time (Study Day)	Assessment	Virus Titre (Log10 Copies/mL)	Did Participant Bleed?	Comments
xxxxxx	xxxxxx	ddmmYYYY / hh:mm (xx)	1 / 2	Xxxxx	Yes / No	xxxxxxxxxxxx

Programming Note: The Limit of Detection and Lower limit of Quantification will be shown in the footnote.

Listing 16.2.6.1.2
Viral Load by Nasal Samples qRT-PCR Derivations

Treatment Group	Participant	IMP administration to planned discharge (hours*Log10 Copies/mL)	IMP administration for 6.5 days (hours*Log10 Copies/mL)	AUC Day 2 to Day 12 (hours*Log10 Copies/mL)	IMP administration to planned discharge (hours*Copies/mL)	Peak Viral Load (from IMP administration to negative test after Day 12) (Log10 Copies/mL)	Time from IMP administration to negative test after Peak measure (days)	Time from Peak measure after IMP administration to negative test after peak measure (days)	Time to Peak Measure (days)
xxxxxx	xxxxxx	XX.XX		XX.XX		XX.XX	XX	XX	XX

* = Censored value.

Note: For the calculation of AUCs, values that are 'Not Detected', 'Detected' or are at or below the limit of quantification have been re-assigned to 0.

Listing 16.2.6.2.1
Viral Load by Nasal Samples Viral Culture Results

Treatment Group	Participant	Sample Type	Sample Collection Date / Time (Study Day)	Assessment	Virus Titre (Log10 Copies/mL)	Comments
xxxxxx	xxxxxx	XXXXXXXXXX	ddmmyyyy / hh:mm (xx)	1 / 2	xxxx	xxxxxxxxxxxxxxxxxxxx

Programming Note: The Limit of Detection and Lower limit of Quantification will be shown in the footnote.

Listing 16.2.6.2.2

Viral Load by Nasal Samples Viral Culture Derivations

Treatment Group	Participant	AUC	IMP administration to planned discharge (hours*Log10 Copies/mL)	IMP administration for 6.5 days (hours*Log10 Copies/mL)	Day 2 to Day 12 (hours*Log10 Copies/mL)	IMP administration to planned discharge (hours*Copies/mL)	Peak Viral Load (from IMP administration to Day 12) (Log10 Copies/mL)	Time from IMP administration to negative test after negative test after Peak measure (days)	Time from Peak measure after IMP administration to negative test after peak measure (days)	Time to Peak Measure (days)
xxxxxx	xxxxxx	XX.XX	XX.XX	XX.XX	XX.XX	XX	XX	XX	XX	XX

* = Censored value.

Note: For the calculation of AUCs, values that are 'Not Detected', 'Detected' or are at or below the limit of quantification have been re-assigned to 0.

Listing 16.2.6.3.1
Symptom Scores from Symptom Diary Card

Treatment Group	Participant	Diary Card Completion		Days from IMP Administration	Assessment	LRT Grades [1]	URT Grades [2]	S Grades [3]	10-item Symptom Score [4]	13-item Symptom Score
		Date / Time (Study Day)	hh:mm (xx)			1 / 2 / 3	X/X/X/X	X/X/X/X/ X	X/X/X/X	Total CFB
xxxxxx	xxxxxx	ddmmyyyy / hh:mm (xx)	XX			1 / 2 / 3	X/X/X/X	X/X/X/X/ X	XX	XX

LRT = Lower respiratory tract. URT = Upper respiratory tract. S = Systemic. CFB = Change from Baseline.

[1] Cough/Shortness of Breath/Chest Tightness/Wheezing

[2] Runny Nose/Stuffy Nose/Sneezing/Sore Throat/Earache

[3] Headache/Malaise/Muscle Joint, Ache/Chilliness, Feverishness

[4] Includes Cough/Shortness of Breath/Runny Nose/Stuffy Nose/Sneezing/Sore Throat/Earache Headache/Malaise/Muscle Joint, Ache.

Note: A total symptom score requires at least one symptom to be scored.

Listing 16.2.6.3.2
Visual Analogue Scale from Symptom Diary Card

Treatment Group	Participant	Diary Card Completion Date / Time (Study Day)	Days from IMP Administration	Assessment	LRT Grades (mm) [1]	URT Grades (mm) [2]	S Grades (mm) [3]
xxxxxx	xxxxxx	ddmmYYYY / hh:mm (xx)	XX	1 / 2 / 3	XX/XX/XX /XX	XX/XX/XX /XX/XX	XX/XX/XX/ XX

LRT = Lower respiratory tract. URT = Upper respiratory tract. S = Systemic.

[1] Cough/Shortness of Breath/Chest Tightness/Wheezing

[2] Runny Nose/Stuffy Nose/Sneezing/Sore Throat/Earache

[3] Headache/Malaise/Muscle Joint, Ache/Chilliness, Feverishness

Listing 16.2.6.3.3
Total Symptom Score: AUC Derivations

Treatment Group	Participant	Total Symptom Score AUC [1]			Total Symptom Score Change from Baseline AUC			Total Symptom Score AUC [2]		
		IMP administration to planned discharge	IMP administration for 6.5 days	Day 2 to Day 12	IMP administration to planned discharge	IMP administration for 6.5 days	Day 2 to Day 12	IMP administration to planned discharge	IMP administration for 6.5 days	Day 2 to Day 12
xxxxxx	xxxxxx	XX	XX	XX	XX	XX	XX	XX	XX	XX

[1] Derivations made using 10-items of the 13-item symptom diary card.

[2] Derivations made using all 13-items of the symptom diary card.

Listing 16.2.6.3.4
Total Symptom Score: Other Derivations

Treatment Group	Participant	Days from IMP administration to planned discharge	Sum Total Symptom Score (from IMP administration to planned discharge)	Peak Total Symptom Score (from IMP administration to planned discharge)	Peak Daily Total Symptom Score (from IMP administration to planned discharge)	Time to Symptom Resolution from IMP administration (days)	Time to Symptom Resolution from Peak Symptom after IMP administration (days)	Time to Peak Total Symptom Score from IMP administration (days)
xxxxxx	xxxxxx	XX	XX	XX	XX	XX	XX	XX

Note: Derivations made for 10-items of the 13-item diary card.

Programming Note: Place the endpoints that are not by study day onto the first row for each participant.

Listing 16.2.6.4.1
Mucus Weight and Tissue Bag Distribution

Treatment Group	Participant	Study Day	Date Collected	Tissue Bag Distribution		Tissues Taken	Total Tissues Taken	Mucus Weight (g)	Total Mucus Weight (g)	Comments
				Time Collected/Dispensed	hh:mm					
xxxxxx	xxxxxx	xx	ddmm/yyyy			xxxx	xxxx	xxxx	xxxx	

Programming note: The Total Mucus Weight and Total Tissues Taken will be listed against the Day 12 observation.

Listing 16.2.6.5.1
Nasopharyngeal Swab: Respiratory Virus Screen/Rapid Viral Antigen Test

Treatment Group	Participant	Sample Collection Date / Time (Study Day)	Result	Comments
xxxxxx	xxxxxx	ddmmyyyy / hh:mm (xx)	Positive / Negative	xxxxxxxx

Listing 16.2.6.6
Plasma PK Parameters

Treatment Group	Participant	Day	PK Parameter	Units	RV299	Comments
xxxxxx	xxxxxx	XXX	XXX	XXX	XXX	xxxxxxxx

Listing 16.2.7
Adverse Events

Treatment Group / Participant /AE Number	MedDRA SOC / Preferred Term [1] / Adverse event (verbatim)	Start Date Time (study day) / Stop Date Time (Study day)	TE [2] / CE [3] / Severity / Frequency [4]	SAE / Serious Criteria [5]	Outcome [6] / Action Taken IMP [7] / Action Taken [8] /	Related to [9] IMP / Challenge Agent / Concomitant medication / Procedure / Other	Comments
xxxxxx / xxxx / xx	xxxxxxxxx/xxxxxx/xxxxxx	ddmmmyyyy hh:mm (xx) / ddmmmyyyy hh:mm (xx)	Yes or No / (xx) / Yes or No / Mild, Moderate, Severe, Life- Threatening / xx	Yes or Blank / xx	x / x / x	x / x / x / x / x	xxxxxxxxxxxx xxxxxxxxxxxx

TE = Treatment Emergent. SAE = Serious Adverse Event.

[1] MedDRA Version 24.0.

[2] An AE occurring on or after the first administration of IMP.

[3] An AE occurring on or after the challenge agent inoculation.

[4] Freq = Frequency. For frequency categories, C = Continuous, I = Intermittent, S = Single Episode.

[5] Serious Criteria: 1 = Death; 2 = Life-threatening; 3 = Hospitalization; 4 = Persistent or significant disability/incapacity; 5 = Congenital anomaly/birth defect; 6 = Other.

[6] Outcome: 1 = Resolved; 2 = Resolved with Sequelae; 3 = Ongoing; 4 = Fatal; 5 = Unknown.

[7] Action Taken IMP: 1 = IMP dosage not changed; 2 = IMP dosage adjusted; 3 = IMP administration temporarily interrupted; 4 = IMP administration discontinued.

[8] Action Taken: 1 = None; 2 = Non-drug therapy given; 3 = Concomitant medication taken; 4 = Participant withdrawn; 5 = Participant hospitalized; 6 = Other; 7 = Not applicable.

[9] Related: 1 = Not Related; 2 = Unlikely Related; 3 = Possibly Related; 4 = Probably Related; 5 = Definitely Related.

Listing 16.2.8.98
Blood Sample Collection

Treatment Group	Participant	Visit	Sample Collection Date / Time (Study Day)	Sample Type(s) [1]	Clinically Significant Result?	Adverse Event associated with Procedure?	Comments
xxxxxx	xxxxxx		ddmmYYYY / hh:mm (xx)	x x x x x x	Yes / No	Yes / No	xxxxxxxxxxxxxxxx

* see Time and Events Schedule.

[1] 1 = Biochemistry, 2 = Cardiac enzymes, 3 = Haematology, 4 = Coagulation, 5 = Thyroid function test,
 6 = Hepatitis B, & C, HIV serology, 7 = Serum pregnancy test, 8 = Serum follicle-stimulating hormone, 9 = Serum markers humoral immunity, 10 = Paxgene.

Listing 16.2.8.99
Haematology

Treatment Group	Participant	Visit	Sample Collection Date / Time (Study Day) ddmm/yyyy hh:mm (xx)	Parameter	Result	Change from Baseline	Units	Lower Limit	Upper Limit	Flag	Comments
xxxxxx	xxxxxx	xxxx		Basophils (%)	x.xx	x.xx	%	x.xx	x.xx	L / H	xxxxxxxxxxxxxxxxxxxx
				Basophils (abs)	x.xx	x.xx	$\times 10^9/L$	x.xx	x.xx		
				Eosinophils (%)	x.xx	x.xx	%	x.xx	x.xx		
				Eosinophils (abs)	x.xx	x.xx	$\times 10^9/L$	x.xx	x.xx		
				Haematocrit	x.xx	x.xx	%	xx	xx		
				Haemoglobin	xxx	xxx	g/L	xxx	xxx		
				Lymphocytes (%)	x.xx	x.xx	%	x.xx	x.xx		
				Lymphocytes (abs)	x.xx	x.xx	$\times 10^9/L$	x.xx	x.xx		
				MCH	x.xx	x.xx	pg	xx.x	xx.x		
				MCHC	xxx	xxx	g/L	xxx	xxx		
				MCV	x.xx	x.xx	fL	xx.x	xx.x		
				Monocytes (%)	x.xx	x.xx	%	xx.x	xx.x		
				Monocytes (abs)	x.xx	x.xx	$\times 10^9/L$	xx.x	xx.x		
				Neutrophils (%)	x.xx	x.xx	%	xx.x	xx.x		
				Neutrophils (abs)	x.xx	x.xx	$\times 10^9/L$	xx.x	xx.x		
				Platelets	xxx	xxx	$\times 10^9/L$	xx.x	xx.x		
				RBC Count	x.xx	x.xx	$\times 10^{12}/L$	x.xx	x.xx		
				Reticulocytes (%)	x.xx	x.xx	%	x.xx	x.xx		
				Reticulocytes (abs)	xx.x	xx.x	$\times 10^9/L$	xx.x	xx.x		
				WBC Count	x.xx	x.xx	$\times 10^9/L$	x.x	xx.x		

L = below lower limit, H = above upper limit.

This layout will be utilised for the following listings:

- Listing 16.2.8.3 Coagulation
- Listing 16.2.8.4 Biochemistry
- Listing 16.2.8.5 Cardiac Enzymes
- Listing 16.2.8.6 Thyroid Function Tests

Listing 16.2.8.100
 Other Laboratory Tests: TDL

Treatment Group	Participant	Visit	Sample Collection Date / Time (Study Day)	Test	Result
xxxxxxx	xxxxxx	xxxx	ddmmmyyyy / hh:mm (xx)	HIV 1 and HIV 2 antibodies Hepatitis A Hepatitis B Hepatitis C FSH Beta HCG (IU/L) Immunoglobulin A antibodies HbA1C (%) HbA1C (mmol/mol)	Positive / Negative Positive / Negative Positive / Negative Positive / Negative xx.x Positive / Negative xx.x xx.x xx.x

L = Low, H = High, ND = Not Done.

Programming Note: Normal Ranges to be displayed in footnote, if available.

Listing 16.2.8.101
Other Laboratory Tests: Urine Pregnancy

Treatment Group	Participant	Visit	Test Date / Time (Study Day)	Participant has data	Result	Comments
xxxxxx	xxxxxx	xxxx	ddmmYYYY / hh:mm (xx)	Yes / No / NA - Male	Positive / Negative	xxxxxxxxxxxxxxxxxxxx

Listing 16.2.8.9.2
Other Laboratory Tests: Drugs of Abuse Screen

Treatment Group	Participant	Visit	Sample Collection Date / Time (Study Day)	Test Performed Time	Drug	Result	Comments
xxxxxx	xxxxxx	xxxx	ddmmmyyyy hh:mm (xx)	hh:mm	Cocaine	Positive / Negative / Not done	
					Cannabinoids	Positive / Negative / Not done	
					Methadone	Positive / Negative / Not done	
					Ecstasy	Positive / Negative / Not done	
					Opiates	Positive / Negative / Not done	
					Benzodiazepines	Positive / Negative / Not done	
					Barbituates	Positive / Negative / Not done	
					Amphetamine	Positive / Negative / Not done	
					Methamphetamine	Positive / Negative / Not done	
					Tricyclic	Positive / Negative / Not done	

Listing 16.2.8.9.
Other Laboratory Tests: Urine Cotinine

Treatment Group	Participant	Visit	Test Performed Date / Time (Study Day)	Result	Comments
xxxxxx	xxxxxx	xxxx	ddmmYYYY / hh:mm (xx)	Positive / Negative	xxxxxxxxxxxxxxxxxx

Listing 16.2.8.9.
Other Laboratory Tests: Alcohol Breath Test

Treatment Group	Participant	Visit	Test Date / Time (Study Day)	Result	Comments
xxxxxx	xxxxxx	xxxx	ddmmyyyy / hh:mm (xx)	Positive / Negative	xxxxxxxxxxxxxxxxxx

Listing 16.2.9.
Urinalysis

Treatment Group	Participant	Visit	Sample Collection Date / Time (Study Day)	Test Performed Time	Parameter	Result [1]
xxxxxx	xxxxxx	xxxx	ddmmmyyyy / hh:mm (xx)	hh:mm	Appearance Bilirubin Blood - Dip Blood - Haemolysed / Non-Haemolysed Colour Glucose Ketones Leukocytes Nitrite Protein Specific Gravity Urobilinogen pH Interpretation Sent for Microscopy Comments	

[1] NCS = Not clinically significant, CS = Clinically significant.

Programming note: The physician interpretation and microscopy (Yes/No) will be shown as an additional row at the end of each assessment, with the interpretation/microscopy outcome shown in the result column.

Programming note: for Blood parameter there is a Haemolysed/Non-Haemolysed as well as a result.

Listing 16.2.9.
Urinalysis (TDL): Microscopy

Treatment Group	Participant	Visit	Sample Collection Date / Time (Study Day)	Urine RBC	Urine WBC	Cellular casts	Granular casts	Hyaline casts	Urine culture
xxxxxx	xxxxxx	xxxx	ddmmYYYY / hh:mm (xx)	xxxxxx	xxxxxx	xxxxxx	xxxxxx	xxxxxx	xxxxxxxx

ND = Not Done, A = Abnormal

Listing 16.2.10
Vital Signs

Treatment Group	Participant	Visit	Date	Assessment	Time Started Supine	Collection Time	Parameter	Result [1]	Change from Baseline	Units	Comments
xxxxxx	xxxxxx	xxxx	ddmmyyyy	1 / 2 / 3	hh:mm	hh:mm	Systolic BP	xxx	xxx	mmHg	
							Diastolic BP	xx	xx	mmHg	
							Heart Rate	xx	xx	bpm	
							Rep. Rate	xx	xx	breaths/min	
							SpO2	xx	xx	%	
							Tympanic temperature	xx.x	xx.x	deg C	
							Interpretation	xxxxxxxx			xxxxxx

[1] NCS = Not clinically significant, CS = Clinically significant.* = tympanic temperature ≥ 37.9 deg C.

Programming note: The physician interpretation will be shown as an additional row at the end of each assessment, with the interpretation outcome shown in the result column. Add * to any temperature result ≥ 37.9 deg C.

Listing 16.2.11
Spirometry

Treatment Group	Participant	Visit	Date / Time (Study Day)	Parameter	Result [1]	Units
xxxxxx	xxxxxx	xxxx	Ddmmyyyy hh:mm (XX)	FEV1 (abs) FEV1 (% Pred) FEV1/FVC Ratio (abs) FEV1/FVC Ratio (% Pred) FVC (abs) FVC (% Pred) FEV1 decreased by > 15% from baseline FEV1 or FVC < 80% of the predicted value?	x.xx xx xx xx x.xx xx Yes / No Yes / No	L % L %

Listing 16.2.12.1
Physical Examination

Treatment Group	Participant	Visit	Date / Time (Study Day)	Parameter	Finding	Comments
xxxxxx	xxxxxx	xxxx	ddmm-yyyy hh:mm (Study Day)	General Appearance Eyes Ears Nose Throat Head and Neck Cranial Nerves/Nervous System Musculoskeletal Skin Cardiovascular Abdomen/GI System Respiratory System Chest - Auscultation Chest - Vocal Resonance Chest - Percussion Other Findings	Normal / Abnormal Not Clinically Significant / Abnormal Clinically Significant / Not Done	

Listing 16.2.12.2
Rhinoscopic Examination

Treatment Group	Participant	Visit	Date / Time (Study Day)	Assessment	Level [1]	Comments
xxxxxx	xxxxxx	xxxx	ddmmmyyyy hh:mm (Study Day)	Nasal Discharge - Left Nasal Discharge - Right Otitis - Left Otitis - Right Pharyngitis Sinus Tenderness - Left Sinus Tenderness - Right New Wheezes, Rhonchi - Left New Wheezes, Rhonchi - Right		

[1] Nasal Discharge: 0 = None, 1 = Clear, serous; scant but slightly increased, 2 = Clear to white, obvious increased volume, + / - minor blood streaks on tissue, 3 = Frankly prudent (yellow or green), or gross blood.

Otitis: NA = Tympanic membrane not visible, 0 = None, 1 = Dull tympanic membrane, 2 = Inflamed, injected tympanic membrane, 3 = Retracted or bulging tympanic membrane, obvious air, fluid level.

Pharyngitis: 0 = None, 1 = Mild and / or patchy erythema, 2 = Marked and / or confluent erythema, 3 = Erythema and purulent exudate.

Sinus Tenderness: 0 = None, 1 = Mild tenderness, 2 = Moderate tenderness, 3 = Severe tenderness or overlying erythema.

New Wheezes, Rhonchi: 0 = None, 1 = Mild wheezes or rhonchi, 2 = Scattered wheezes or rhonchi, 3 = Widespread wheezes.

Listing 16.2.111
ECG

Treatment Group	Participant	Visit	Date	Time Started in Resting Position	Time Performed	Parameter	Result [1]	Units	Comments
xxxxxxx	xxxxxx	xxxx	ddmmYYYY	hh:mm	hh:mm	HR	xxx	bpm	xxxxxx
						PR	xxx	ms	
						QRS	xxx	ms	
						QT	xxx	ms	
						QTc	xxx	ms	
						QTcB	xxx	ms	
						QTcF	xxx	ms	
						RR	xxx	ms	
						Interpretation	Normal / Abnormal NCS / Abnormal CS		

[1] NCS = Not clinically significant, CS = Clinically significant.

Programming note: The physician interpretation will be shown as an additional row at the end of each assessment, with the interpretation outcome shown in the result column.

Listing 16.2.14
Visit Dates

Treatment Group	Participant	Visit	Date	Source of Unscheduled Visit	Comments
xxxxxx	xxxxx	xxxx	ddmm/yyyy	xxxxxxxxxx	xxxxxxxxxxxxxx

Programming note: Unscheduled visits and visit information will be taken from specific database modules and the "Reason for additional collection" will be placed in the comments column in this listing.

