10.7.1. Primary Endpoint

10.7.1.1 Main Analysis

The primary endpoint is the AUC of RSV-A Memphis 37b viral load measured in nasal washes by qRT-PCR, from the last measurement collected prior to the first administration of IMP until the last measurement collected up to the morning of Day 12 (Quarantine discharge). The viral load data will be supplied as \log_{10} copies/mL and will be used for this main analysis and to calculate the AUC using the trapezoidal rule [1].

The AUC will be summarised for RV299 and placebo using descriptive statistics and an ANCOVA with treatment group as a main effect and the baseline value as a covariate. The baseline value will be the qRT-PCR viral load value from the last measurement collected prior to the first administration of IMP. The treatment comparison will be presented, including the LS mean treatment difference with the corresponding two-sided 95% confidence interval and p-value. The equivalent Wilcoxon rank-sum tests will be provided in place of the ANCOVA where the assumptions of the parametric test are not met.

As nasal washes are scheduled to be taken twice daily for Days 2 to 11 (and once on Day 12), in order to calculate the AUC, the actual time that the assessment was collected will be used within the AUC calculation. The AUC calculation will be based on the available non-missing assessment values between the start and end of the defined AUC time period. However, for an AUC to be derived, a participant should have at least one non-missing data recording at the start of the AUC period (e.g. date of first administration of IMP) and also at the end of the AUC time period (e.g. Day 12). In addition, the participant should have at least 1 non-missing data recording on each day between the start and end of the defined AUC time period (i.e. at least 1 out of the 2 possible assessments on each Day)). Any missing data will be reviewed at the BDRM, for its potential impact on this endpoint, and any decisions to exclude participants as a result of these criteria will be documented in the BDRM minutes. For the reporting of AUC, where appropriate, qRT-PCR values that are 'Not Detected' or 'Detected' will be re-assigned using the substitution values shown in the table in Appendix 15.1.

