10.7.2.4 Clinical Symptom-Related Endpoints

Area under the Curve over Time of Total Clinical Symptoms (TSS-AUC) as Measured from 10 Symptoms within the Graded Symptom Scoring System Collected 3 Times Daily Starting at Initial Administration of IMP up to Planned Discharge from Quarantine

Total symptom scores (from 10 items of the 13-item symptom diary card) will be used to calculate the AUC, from the assessment nearest to the time of the first administration of IMP (can be prior to or after dosing, depending on whether dosed in the morning or evening), i.e. baseline, until Day 12 (Quarantine discharge), for each participant using the trapezoidal rule [1].

Symptoms are assessed 3 times daily for Day 1 to Day 11 (and once for Day 12) and recorded on the symptom diary cards at each assessment. The following types of symptoms are recorded (on a grading scale, 0 to 3 (or 0 to 4 for the Shortness of Breath symptom)):

- Upper Respiratory Tract (URT): runny nose, stuffy nose, sore throat, sneezing, earache.
- Lower Respiratory Tract (LRT): cough, shortness of breath.
- Systemic: headache, malaise, muscle/joint ache/stiffness.
- Not used for analyses: chilliness/feverishness, chest tightness, wheeze.

A total symptom score will be derived for each participant, separately for each assessment (symptom diary card) on each day (Day 0 to Day 12) as follows:

- For each assessment, sum the 10 observed symptom grade values for each symptom diary card to obtain a total symptom score for each symptom diary card. If the participant does not have all 10 observed values on a specific symptom diary card being considered, then total symptom score will not be calculated for that symptom diary card. It is expected that participants will not have missing data.
- The AUC calculation will be based on the available non-missing calculated total symptom scores between the start and end of the defined AUC time. However, for an AUC to be derived, the participant should have at least 1 non-missing calculated total symptom scores at the start of the AUC period (e.g. date of first dose of IMP) and also at the end of the AUC time period

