Table 14.2.2.4.1 Time to Peak RSV Challenge Virus qRT-PCR following Initial Administration of IMP - ITT-I Population

Table 14.2.2.7.1 Time to First Confirmed Undetectable Assessment of RSV Challenge Virus after Peak Measure by Viral Culture starting from Initial Administration of IMP - ITT-I Population

Table 14.2.2.8.1 Time to First Confirmed Undetectable Assessment of RSV Challenge Virus by Viral Culture starting from Peak Measure - ITT-I Population

Where appropriate, these tables may be repeated on the ITT-A, ITT-B, ITT and PP Populations as .2, .3, .4 and .5 respectively.

Table 14.2.3.1.1
 AUC of Total Symptom Score from 10-Item Diary Card from First Administration of IMP to Quarantine Discharge
 ITT-I Population

AUC (hours*scores)	Treatment Group	
	RV299 (N=xx)	Placebo (N=xx)
n	XX	XX
Mean (SD)	XX.X (XX.XX)	XX.X (XX.XX)
GM (GSD)	XX.X (XX.XX)	XX.X (XX.XX)
%CV	XX.XX	XX.XX
Median	XX.X	XX.X
Q1, Q3	XX.X, X.XX	XX.X, X.XX
Min, Max	XX, XX	XX, XX
Difference in LS means [1]	XX.XX	
95% Confidence interval for difference	XX.XXX, XX.XXX	
P-value [1]	X.XXX	

[1] Comparison of RV299 and placebo using an ANCOVA with treatment group as a fixed effect and baseline viral load as the covariate.

Note: Total symptom scores at the time of the first administration of IMP can be prior to or after dosing, depending on whether dosed in the morning or evening.

Note: GM is derived by antilog(mean(exp(TSS-AUC + 1))) - 1.

This table may be repeated on the ITT-A, ITT-B, ITT and PP Populations as .2, .3, .4 and .5 respectively.

This layout will be utilised for the following tables:

Table 14.2.3.1.2 AUC of Total Symptom Score from 10-Item Diary Card from First Administration of IMP for 6.5 Days - ITT-I Population

Table 14.2.3.1.3 AUC of Total Symptom Score from 10-Item Diary Card from Day 2 to Day 12 - ITT-I Population

Table 14.2.3.2.1 AUC of Total Symptom Score Change from Baseline from 10-Item Diary Card from First Administration of IMP to Quarantine Discharge - ITT-I Population

Table 14.2.3.2.2 AUC of Total Symptom Score Change from Baseline from 10-Item Diary Card from First Administration of IMP for 6.5 Days - ITT-I Population

Table 14.2.3.2.3 AUC of Total Symptom Score Change from Baseline from 10-Item Diary Card from Day 2 to Day 12 - ITT-I Population

Table 14.2.3.4.1 Peak Total Symptom Score from 10-Item Diary Card from First Administration of IMP to Quarantine Discharge - ITT-I Population

COI

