15. APPENDICES

15.1. Study VIR-CST-001 assay cut-offs and reporting

Analysis	Assay	Associated units	Assay Reporting		
			Result	Reported result	S-cubed assigned value
RSV titre (Viral Load)	RSV Viral Culture assay (plaque assay)	\log_{10} PFU/mL	ALOQ	ALOQ	6.34
			Quantifiable Titre	Value	Use reported value
			DETECTED	DETECTED	1.00
			NOT DETECTED	NOT DETECTED	0
			INVALID	INVALID	Missing data point
			NOT TESTED	N/A	Missing data point
RSV titre (Viral Load)	qRT-PCR (in saline matrix)	\log_{10} Copies/mL	Quantifiable Titre	Value	Use reported value
			DETECTED	DETECTED	1.69
			NOT DETECTED	NOT DETECTED	0
			INVALID	INVALID	Missing data point
			NOT TESTED	N/A	Missing data point
RSV antibody titre	RSV Neutralisation Assay (virus focus reduction neutralisation assay)	None	Quantifiable Titre	Value	Use reported value
			>4209	>4209	4209
			<156	<156	78
			NDA	NDA	10
			INVALID	INVALID	Missing data point
			NOT TESTED	N/A	Missing data point

N/A = not applicable; NDA = no detectable antibody.

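### Footnotes to the viral-load derivation listings set Detected results to 0 in the AUC, against 1.69 (qRT-PCR) and 1.00 (culture) in the SAP's own rule; the symptom-score shells have smaller conflicts

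*SAP*

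**What the plan says.** **Detected results in the AUC.** SAP Section 10.7.1.1, which defines the primary analysis, states that "qRT-PCR values that are 'Not Detected' or 'Detected' will be re-assigned using the substitution values shown in the table in Appendix 15.1". For qRT-PCR that table has the row "DETECTED DETECTED 1.69" in log10 copies/mL, with Not Detected at 0. For viral culture it gives Detected as 1.00 log10 PFU/mL, Not Detected as 0, and results above the limit of quantification as 6.34. The shells for Listings 16.2.6.1.2 and 16.2.6.2.2, which display each participant's AUCs, both carry the footnote "For the calculation of AUCs, values that are 'Not Detected', 'Detected' or are at or below the limit of quantification have been re-assigned to 0".

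**Symptom total.** Section 10.7.2.4 derives no total from an incomplete card: where someone "does not have all 10 observed values on a specific symptom diary card being considered, then total symptom score will not be calculated". The footnote to Listing 16.2.6.3.1 says "A total symptom score requires at least one symptom to be scored".

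**Geometric mean and SD.** Section 10.1.2 adds a constant, averages the log10 values, takes the antilog and subtracts the constant. Its geometric SD formula has no constant. The note under Table 14.2.3.1.1 says "GM is derived by antilog(mean(exp(TSS-AUC + 1))) - 1". That layout, with its GM (GSD) row, is reused for the change-from-baseline AUC tables (14.2.3.2.1 to 14.2.3.2.3) and for peak score (14.2.3.4.1). GM rows also appear in the change-from-baseline columns of Table 14.2.3.6.1.

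SAP Section 11 lists none of these differences as an intended change.

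**The concern.** The first conflict touches the primary endpoint. Listing 16.2.6.1.2 shows the primary AUC and its three sensitivity versions for each participant. Either its footnote describes what was programmed, and the primary values depart from Section 10.7.1.1, or it does not, and the listing gives readers a false account of the primary data.

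The footnote also fits badly with the infection definition. Section 9.2 counts a Detected result as a positive detection. Under the footnote, a participant who entered the ITT-I population on two Detected results, with every other wash Not Detected, would have a primary AUC of exactly 0.

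The other conflicts matter less. Scoring a partial diary card as a total treats missing items as zero and so understates symptoms. The geometric-mean note and the geometric SD formula can give impossible or undefined values, but in descriptive rows only.

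**Working it through.** The documents give no AUC mean, SD or effect size for this point, so there is no planned figure to reproduce. The check sizes each conflict from the SAP's own rules.

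**1. AUC per Detected wash.** Inputs: trapezoidal rule and twice-daily washes (Section 10.7.1.1); about 12 h between washes (schedule of events); substitution values (Appendix 15.1). With spacing h, an interior value v contributes v x h and an end value contributes v x h/2.

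| Assay | Appendix value | Footnote value | Gap, interior wash | Gap, end wash |
|---|---|---|---|---|
| qRT-PCR | 1.69 | 0 | 1.69 x 12 = 20.28 | 10.14 |
| Culture | 1.00 | 0 | 1.00 x 12 = 12.0 | 6.0 |

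For qRT-PCR, two interior Detected washes give 40.56, four give 81.12 and six give 121.68 h*log10. The ceiling, with every wash Detected, depends on the window:
- First dose on the evening of Day 5: 14 washes, 13 x 12 = 156 h, and 1.69 x 156 = 263.64.
- First dose on the evening of Day 2: 20 washes, 19 x 12 = 228 h, and 1.69 x 228 = 385.32.

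An illustration with an assumed profile, not taken from the documents: 16 washes at 3, 4, 5, 5.5, 5.5, 5, 4.5, 4, 3.5, 3, 2.5, then four Detected, then one Not Detected. The AUC is 609.1 under Appendix 15.1 and 528.0 under the footnote, a fall of 81.1, or 13%.

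**2. Effect on the treatment difference.** These gaps are within a participant, and the substitution applies to both arms. Let m be the mean number of interior Detected washes per participant in an arm. Moving from the appendix to the footnote changes the RV299-minus-placebo difference in mean AUC by about -20.28 x (m for RV299 - m for placebo). Equal counts give 0; a difference of one wash gives 20.28; a difference of two gives 40.56. The figure is approximate because the analysis adjusts for baseline viral load and uses actual sampling times. Neither document gives m, so neither the size nor the direction of the shift can be computed.

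**3. Symptom total.** The ten-item maximum is 9 x 3 + 4 = 31, since shortness of breath runs to 4. Suppose one item other than shortness of breath is scored 1 and nine are missing. The footnote allows a total of 1. The true total could lie anywhere from 1 to 1 + 8 x 3 + 4 = 29. Section 10.7.2.4 would give no total.

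**4. Geometric mean and SD.** For assumed values 0, 1, 2, 3 and constant 1:
- Section 10.1.2: (1 x 2 x 3 x 4)^(1/4) - 1 = 1.21.
- Table note: the mean of exp(1), exp(2), exp(3), exp(4) is 21.2. Its antilog less 1 is about 1.6e9 (natural) or 1.6e21 (base 10), both far above the largest value, 3.
- In double precision, exp() overflows once TSS-AUC + 1 reaches 710. That is an average score of 709/156 = 4.5 over 156 h, or 709/228 = 3.1 over 228 h, out of a possible 31.

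The geometric SD in Section 10.1.2 takes log10 of the raw value, so any zero makes it undefined. Zeros are expected: Section 10.7.2.4 assigns a peak of 0 to participants without symptoms. Change-from-baseline values can be negative, and once the value plus the constant is zero or below, neither statistic exists.

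**The case against.** The strongest reply is that the SAP already settles the matter. The section defining the primary endpoint states the substitution rule and points to a table of explicit values. The conflicting text is a footnote in participant-listing shells, and the shell for the primary results table, 14.2.1.1, has no such note. Shell text is out of step with the body elsewhere too: the adverse event listing cites MedDRA 24.0 where Section 10.9.1 cites 25.0. A programmer working from Section 10.7.1.1 would use 1.69. This largely stands. A reader might infer that the primary endpoint is undefined or has two equally valid readings, and the documents do not support that.

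The objection does not remove the conflict. Section 10.1.2 refers to the shells for the format and content of each presentation, and the SAP does not say which text governs when the two disagree.

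A reader might also set the 81 or 122 units from four or six Detected washes against a hoped-for treatment effect and conclude that the artefact could equal it. That compares a within-participant shift with a between-arm difference, and no effect size or placebo mean is available in either document. Nor do the documents show that Detected results gather in the decline phase of infection; that is plausible but remains an inference.

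On the smaller points, Section 10.7.2.4 expects no missing diary data, so the diary conflict may never operate. The geometric mean and SD do not enter the ANCOVA or the Wilcoxon test.

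**Conclusion.** The conflict is real and should be fixed, with the two Detected footnotes first. Programming the footnote would lower a participant's primary AUC by 20.28 h*log10 for each interior Detected wash and 10.14 for one at either end, at nominal 12 h spacing; for culture the figures are 12.0 and 6.0. Programming Appendix 15.1 leaves the primary result as intended but the listing wrong. The shift in the treatment difference is about 20.3 times the between-arm difference in mean interior Detected counts. It is zero if the counts are equal and otherwise unknown from these documents.

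The remaining points are minor. The diary footnote matters only if items are missing. The geometric-mean note, the missing constant in the geometric SD and the GM/GSD entries for change from baseline affect descriptive statistics only.

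**What to change.** Before unblinding:

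- Replace the footnotes to Listings 16.2.6.1.2 and 16.2.6.2.2 with: *Non-numeric results are substituted as in Appendix 15.1.* For culture this must cover the above-quantification value of 6.34, and the footnote should also cite the Section 10.7.2.3 rule that a missing culture result becomes Not Detected when the matching qRT-PCR result is Not Detected. Appendix 15.1 has no separate row for values at or below the limit of quantification, so that phrase should go.
- Check that the AUC program uses the Appendix 15.1 values for both assays.
- Change the diary footnote to: *The 10-item total requires all 10 items; the 13-item total requires all 13.* Listing 16.2.6.3.1 shows both scores, and the readable SAP text gives a completeness rule only for the first.
- Replace the geometric-mean note with the Section 10.1.2 log10 formula, and add the same constant inside the geometric SD.
- Drop GM and GSD from change-from-baseline tables and columns.

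The cost is text edits and one programming check. Data collection is unaffected.
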